#### **(3) Sample size:**

Sample size estimation based on the core principles of predictive model development (TRIPOD statement). The core strategy follows an outcome event-driven approach, focusing on the number of target events (e.g., disease positivity). Using the method recommended by Riley et al., the minimum sample size was calculated by the R language pmsampsize package. The calculation parameters include: (1) expected model discrimination (e.g., AUC is preset to 0.8);(2) the estimated number of predictors in the final model (k according to the literature and pre-experiments); and (3) the expected effect strength of the predictor (conservative estimates). At the same time, considering the high-dimensional characteristics of radiomics, the total sample size meets the following empirical criteria: (1) the number of events  $\geq$  (10 times k (EPV principle); (2) Total sample size  $\geq$  (10 times k). The final sample size was increased by 10-20% to compensate for missing data and heterogeneity. Multicenter image heterogeneity was included in the sample size calculation, and the sample size adequacy was verified by Bootstrap sampling.

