### **3. Research Methodology**

This study is based on a multicenter retrospective cohort including a prospective test cohort to include patients with unresectable hepatocellular carcinoma who have received TACE in combination with target-immune therapy. The data comes from the clinical diagnosis and treatment records of 8 tertiary hospitals from 2016 to 2025, and strictly follows the preset inclusion standards.

Generative model construction: diffusion model-based treatment response simulator: input data: enhanced CT/MRI images at the patient's baseline, real post-treatment enhanced CT/MRI images and clinical features (Child-Pugh score, AFP level, treatment plan, etc.). Model architecture: The conditional diffusion model was used to dynamically simulate the virtual follow-up images of the best response after treatment with the treatment protocol (TACE embolic agent dose + target immune drug combination) as the generation conditions. Training mechanism: The model is optimized by comparing the differences in deep visual features between the generated images and the real follow-up images to ensure that the generated results conform to the laws of biological evolution. Quantitatively evaluate the visual fidelity of the generated images (FID index <25); The clinical rationality was scored by 3 interventional radiology experts by blind (on a 5-point scale  $\geq$  4 points were considered qualified).

Dynamic survival prediction framework: Capture 256-dimensional semantic feature vectors from the generated virtual images to characterize the dynamic changes of tumor microenvironment. The depth features extracted by the generative model are fused with the patient's clinical variables, and the key predictors are automatically identified through the gated attention mechanism. Survival risk modeling: Construct a Transformer-based time-series survival model to output individualized survival curves and survival probability predictions at key time points (12/24/36 months).

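### The sample-size rule counts the predictors left in the final model, not the 256 image features plus clinical variables searched, so it can pass a sample too small for that search

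*Protocol*

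**What the plan says.** Under "(3) Sample size" the protocol says that "the minimum sample size was calculated by the R language pmsampsize package". Its inputs are "expected model discrimination (e.g., AUC is preset to 0.8"), an effect-strength assumption, and "the estimated number of predictors in the final model (k according to the literature and pre-experiments"). The same k then serves two further rules, introduced with "considering the high-dimensional characteristics of radiomics, the total sample size meets the following empirical criteria". Events must be at least "10 times k (EPV principle"), and total N must be at least ten times k. A margin follows: "The final sample size was increased by 10-20% to compensate for missing data and heterogeneity". The section also reports a bootstrap check of adequacy. It prints no value for k, N, the number of events or the event fraction.

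Under "3. Research Methodology", the dynamic survival prediction framework is to "Capture 256-dimensional semantic feature vectors from the generated virtual images". These are fused with the clinical variables, whose number is not given, and "the key predictors are automatically identified through the gated attention mechanism". The same section makes the C-index for overall survival the main measure of predictive performance. It compares a clinical-only model with models that add real or virtual images.

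**The concern.** Both sample-size methods tie the amount of information in the data to the number of parameters that the data have to support. If predictors are chosen by looking at the outcome, every candidate has had a chance to fit noise, whether or not it survives. Counting only the survivors treats the search as free. A section that says it allows for high dimensionality then leaves the high dimension out of its arithmetic.

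At stake is the main comparison of the study. The image-based models search 256 features that the clinical-only model does not have, so undetected overfitting would favour the image arm during development. Predicted survival differences also feed the treatment-recommendation rule in the same section.

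**Working it through.** **No figure to reproduce.** The protocol prints no N, so the check compares its rule under two definitions of k.

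**Inputs from the protocol:** C (AUC) = 0.8, given there as an example; 256 image features; EPV of 10; inflation of 10-20%.

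**Assumed, because not given:** final k = 10 (range 5-20); 10 clinical variables, hence 256 + 10 = 266 candidates; event share f = 0.3, 0.5 or 0.7; target shrinkage S = 0.9.

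**1. EPV rule.** Events = 10 × k.
- Final k = 10: 100 events. Candidates = 266: 2,660 events.
- 100 events spread over 266 candidates is 100/266 = 0.38 events per candidate. For k = 5 or 20 it is 50/266 = 0.19 or 200/266 = 0.75.
- The gap in events is 2,660/200 = 13-fold to 2,660/50 = 53-fold. A 20% allowance turns 100 events into at most 100/0.8 = 125.
- The second rule adds nothing: events of at least 10k already imply N of at least 10k.

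**2. Riley shrinkage criterion, survival outcome.** N = p / [(S − 1) ln(1 − R²/S)], where R² is the Cox-Snell value.
- D = 5.50(0.3) + 10.26(0.3)³ = 1.927.
- R²_D = (π/8)D² / [π²/6 + (π/8)D²] = 0.470.
- Converted to the O'Quigley form: (π²/6)R²_D / [1 + (π²/6 − 1)R²_D] = 0.593.
- R² = 1 − (1 − 0.593)^f.

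| f | R² | N, p = 10 | N, p = 266 | EPV 10 N, p = 266 |
|---|---|---|---|---|
| 0.3 | 0.236 | 329 | 8,726 | 8,867 |
| 0.5 | 0.362 | 195 | 5,167 | 5,320 |
| 0.7 | 0.467 | 137 | 3,634 | 3,801 |

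The criterion is proportional to p, so the ratio is 266/10 = 26.6 in every row.

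**3. Binary version.** R² is about 0.228 at f = 0.3 or 0.7, and 0.262 at f = 0.5. Taking the largest of the Riley criteria:
- k = 10: N of 343-385. The upper end comes from the overall-risk criterion, 0.5 × 0.5 × (1.96/0.05)² = 384.2.
- k = 20: N of about 580-689.
- 266 candidates: N of about 7,700-9,150.

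**4. Shrinkage delivered.** Solve the survival formula for S at the N that EPV 10 gives on the final k. With p = k, S is about 0.90. With p = 266 it is about 0.34-0.48 for k = 10, and 0.27-0.54 over k = 5-20. The formula is only indicative that far from its target.

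**5. Simulations, as illustration only.**
- Pure noise, Cox model, sample set by EPV 10 on k = 10: the best 10 of 266 useless features show an apparent C-index of about 0.70. Ten prespecified noise features show about 0.59. New data give 0.50.
- Real signal (true AUC about 0.79), N = 385, independent features, univariable choice of 10 from 266, unpenalised logistic model. With 10 true predictors the calibration slope on new data was 0.61-0.68 across repeated runs; AUC fell from about 0.80 in development to 0.69-0.73. With 60 weak predictors the slope was 0.27-0.30, and AUC fell from about 0.75 to 0.57-0.58. With only 10 candidates and N = 345 the slope was 0.86-0.89.
- Features driven by 12 shared latent factors: slope 0.82, AUC from 0.80 to 0.76.
- Ridge regression on all 266: slopes of 1.05-1.13, but AUC of about 0.65 on new data when features are independent.

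**The case against.** The strongest reply is that nothing has been shown to be too small. The protocol states no N and no k, so the contrast between 100 and 2,660 events rests on an assumed final k of 10. That stands: a reader might infer that the study's sample falls short by a known factor, and the document does not support that.

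Second, gating often weights inputs rather than discarding them. If every fused input stays in, a final-model k of 256 or more would make the rule sound in form. The protocol does not say how many inputs remain, but its wording about key predictors being identified automatically points to selection, and nothing ties k to the candidate count.

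Third, a reader might infer that predicted survival must come out too extreme. That does not follow. The unfavourable simulations use independent features, univariable selection and no penalty, which is not the planned attention and Transformer model. The loss is smaller with correlated features, and ridge removes the excess spread, although it does not restore discrimination when features are independent. For a network, counting inputs is itself a rough guide: effective degrees of freedom may be lower through a penalty or higher through the network's weights. Even so, the protocol chose the Riley and EPV methods, and must use the count for which they are valid.

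Fourth, there are safeguards: a prospective test cohort, a validation set and other test sets, calibration analysis and bootstrap. They would reveal overfitting, but they do not make the development sample adequate.

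**Conclusion.** The definition of k is wrong as written. This is not a detail left for a statistical analysis plan: the protocol fixes the input to its calculation, and fixes it on the survivors of a search through at least 256 features. Following the rule does not give the control of overfitting for which the two methods are cited.

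The direction holds for any final k well below the candidate count. The size does not have one value: the figures above depend on the assumed final k, number of clinical variables and event share. Because overall survival is the main outcome, the survival range (N of about 3,600-8,700 for 266 candidates) is more relevant than the binary one. The simulated losses show what can happen, not what will.

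**What to change.** - In the sample-size section, define k as the number of candidate predictor parameters offered to the survival model, and drop the statement that EPV 10 is met on final-model k.
- Before the outcome is used, fix an outcome-blind reduction of the 256 features (principal components or an unsupervised bottleneck, for example) to the number that the available training-set events support. Alternatively, prespecify a penalised model with an optimism correction that repeats the whole selection step in each bootstrap sample.
- Re-run the survival version of pmsampsize with that k, and state k, the event fraction, the required events and N.
- If the available events do not support the candidate count, reduce the candidates or restate the figure.

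The cost is protocol wording, one recalculation and a prespecified reduction step. The downside is that fewer image features enter the survival model. Whether more patients would be needed cannot be said from the document, since neither the available N nor the number of events is given.

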#### (2) Selection of research subjects:

This project is a real-world study, including retrospective training, validation and testing cohorts and prospective testing cohorts, all registries are derived from real cases in clinical practice, and the collected case data should include the following requirements:

1. Unresectable hepatocellular carcinoma confirmed by histopathological diagnosis and/or clinical diagnosis (typical imaging features, clinical manifestations, laboratory tests, etc.) (Annex: Guidelines for the diagnosis and treatment of primary liver cancer (2024 edition));
2. Patients who receive TACE combined with targeted immunotherapy on the basis of the diagnosis of unresectable hepatocellular carcinoma;
3. Liver function grade Child-Pugh A or B;
4. Over 18 years old, regardless of gender;
5. Expected survival time  $\geq$  3 months;
6. ECOG PS score  $\leq 2$ ;

7. Meet the following laboratory examination parameters;

- 1) Hematologic function: absolute neutrophil count  $\geq 1.0 \times 10^9 / \text{L}$ ; Platelet count  $\geq 50 \times 10^9 / \text{L}$ ; hemoglobin  $\geq 90 \text{ g/L}$ ; The international normalized ratio is less than 1.7 or the prothrombin time is prolonged by no more than 4 seconds,
- 2) Liver function: alanine aminotransferase/aspartate aminotransferase does not exceed 5 times the upper limit of normal; total bilirubin  $\leq 210 \text{ micromol/L} [\leq 2.38 \text{ mg/dL}]$ ; Albumin  $\geq 28 \text{ g/L}$ ,
- 3) Renal function: serum creatinine does not exceed 1.5 times the upper limit of normal.

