Treatment decision support systems: causal effects deduction: quantifying the expected survival benefit of different treatment regimens (eg, TACE + lenvatinib + pembrolizumab versus TACE + bevacizumab + atezolizumab) using a counterfactual analysis framework. Generate a heat map of treatment regimen comparisons to visualize simulated tumor regression differences. Decision rule: When the median survival benefit of a regimen is expected to be more than 3 months and the confidence probability is greater than 80%, the system preferentially recommends the regimen.

Model validation strategy: Stratified by study center, randomly assigned to the training set (70%), validation set (30%), and multiple test sets.

Survival prediction assessment: main indicators: C-index evaluation of overall survival prediction

accuracy; Secondary indicators: 12/24/36 months of time dependence on AUC to assess discriminant ability at a specific time point; Calibration analysis: The Brier score quantifies the prediction error, and the calibration curve evaluates the risk prediction consistency. Comparative experimental design: baseline model (clinical variables only); benchmark model + real follow-up images; Datum model + generate model virtual image.

Reproducibility & Ethics: The model code and preprocessing process are published in the public repository (GitHub). The self-service resampling method (1000 times) was used to calculate the 95% confidence interval.

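### The 10-events-per-predictor rule is set on the total sample, but the model is fitted on at most 70% of it, so the rule guarantees only about 7 events per predictor in the training set

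*Protocol*

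**What the plan says.** The Protocol, section (3) Sample size, uses two approaches side by side.

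- **pmsampsize.** The text says "the minimum sample size was calculated by the R language pmsampsize package", with an AUC preset to 0.8. It reports no result and does not say which cohort the minimum refers to. The number of predictors is described as "the estimated number of predictors in the final model (k according to the literature and pre-experiments"), without a figure.
- **Empirical rules.** The section adds that "the total sample size meets the following empirical criteria: (1) the number of events" is at least "10 times k (EPV principle"), and that the total number of patients is also at least ten times k. Both are minimum requirements, and both are attached to the total.

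An uplift follows: "The final sample size was increased by 10-20% to compensate for missing data and heterogeneity".

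Section 3, Research Methodology (model validation strategy), states that patients are "randomly assigned to the training set (70%), validation set (30%), and multiple test sets". Section (2), Selection of research subjects, describes the study as "including retrospective training, validation and testing cohorts and prospective testing cohorts". Nowhere does the Protocol say that the events-per-predictor rule must hold in the training set.

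**The concern.** An events-per-predictor rule is there to limit overfitting, and overfitting depends on the data used to fit the model. Events in patients held out for validation or testing do nothing to stabilise the fit. A rule met on the total and followed by a 70/30 split therefore gives less protection than it appears to give.

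The uplift does not close the gap. It is reserved for missing data and heterogeneity, the exclusion criteria remove incomplete cases, and even a full 20% is too small to offset a 30% hold-out.

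The training share is also uncertain. Training and validation already make 100% before any test set is named, so if the retrospective test sets come from the same total, less than 70% of it is left for fitting.

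At stake is the number of predictors that the team believes the data can carry. The sample size section itself points to the high dimensionality of radiomics, so this limit matters here.

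**Working it through.** **Inputs from the Protocol:** at least 10 events per predictor on the total; uplift 10-20%; training share 70%; AUC 0.8. No sample size, event count, k or event rate is given, so there is no stated sample size to reproduce.

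**1. Guaranteed events per predictor in training.** Formula: 10 x uplift factor x training share, with the total exactly at the rule's minimum.

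| Uplift left after missing data | Calculation | Events per predictor |
|---|---|---|
| none | 10 x 1.0 x 0.70 | 7.0 |
| full 10% | 10 x 1.1 x 0.70 | 7.7 |
| full 20% | 10 x 1.2 x 0.70 | 8.4 |

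If the 20% is instead applied as division by 0.8, the top figure is 10 x 0.70 / 0.8 = 8.75. Offsetting the split alone needs a factor of 1/0.70 = 1.43, and 1.2 x 0.70 = 0.84 falls short of 1.

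**2. Test sets inside the total.** Assume that a share t goes to test sets first and that the remainder is split 70/30. Formula: 10 x uplift factor x 0.70 x (1 - t).

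- t = 0.10: 6.3 with no uplift left, 7.56 with the full 20%.
- t = 0.30: 4.9 with no uplift left, 5.88 with the full 20%.

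The shares t are assumptions, since the Protocol gives none.

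**3. Could pmsampsize be the larger requirement?** Assumptions: binary outcome, AUC 0.8, shrinkage target 0.90, optimism limit 0.05, and the minimum applied to the total. The event proportions are also assumed.

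| Event proportion | Events per predictor, total | x 0.70 in training |
|---|---|---|
| 0.1 | 7.6 | 5.3 |
| 0.2 | 8.8 | 6.2 |
| 0.3 | 10.2 | 7.2 |
| 0.4 | 12.1 | 8.5 |
| 0.5 | 14.6 | 10.2 |
| 0.6 | 18.2 | 12.8 |

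Below a proportion of about 0.3 the rule of ten is the stricter one, and the training floor stays at 7.0. At about 0.5 or more, pmsampsize leaves at least 10 events per predictor in training even after the split.

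**4. What the split does to pmsampsize's own target, if its minimum is on the total.** Shrinkage criterion: N = k / ((S - 1) ln(1 - R2/S)). Take an assumed target S = 0.90 and an assumed Cox-Snell R2 of 0.2. Then N/k = 1 / (0.1 x 0.2513) = 39.8. Solving for S at the training size:

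- 0.70 x 39.8 = 27.9 patients per predictor: S = 0.86
- 0.77 x 39.8 = 30.6: S = 0.87
- 0.84 x 39.8 = 33.4: S = 0.88

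R2 of 0.1 or 0.3 gives the same values to two decimals.

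**5. Total needed for 10 events per predictor in training.** 10 / 0.70 = 14.3 total events per predictor. With the uplift on top this is 14.3 x 1.1 = 15.7 to 14.3 x 1.2 = 17.1. For k = 20, that is 286 total events before uplift instead of 200.

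**The case against.** The strongest reply is that no stated number is wrong. The rule is a minimum, and the section gives no sample size, k or event count. A reader might infer that the training set will have 7.0 to 8.4 events per predictor. The Protocol does not support that, because those figures are only what this one rule guarantees. This part of the reply stands.

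A reader might also infer that the shortfall below 10 arises for any k and any outcome. Step 3 shows otherwise: if events are common, pmsampsize can require enough to leave 10 or more in training. That is plausible for progression-free survival, since the background cites medians of about 15 months against prediction horizons of 12, 24 and 36 months. This stands too, but it does not rescue the plan as written. If pmsampsize governs and was sized on the total, 70% of its minimum misses its own target. If it was sized on the training set, that criterion is met, but the section does not say so.

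The shrinkage figures should not be read as a departure from a stated promise. The Protocol names no shrinkage target; 0.90 is an assumption here.

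Two further replies carry some weight. Validation and test sets, calibration and bootstrap intervals would reveal some of the overfitting. And k counts predictors in the final model, while the survival framework draws on 256-dimensional image features, so changing the base of the rule does not remove all overfitting risk. Both lower the severity. Neither puts the rule on the right base.

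The section also says that bootstrap sampling verified adequacy, but it reports no result and names no cohort.

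**Conclusion.** The point holds as a misplaced base for a stated safeguard. The Protocol sets its 10-events-per-predictor rule on the total and fits the model on at most 70% of that total. At its minimum the rule guarantees about 7.0 events per predictor in training, or 7.7 to 8.4 if the full 10-20% uplift survives. It guarantees less if test sets are drawn from the same total: 4.9 to 7.6 under assumed test shares of 10-30%.

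These are floors, and the achieved ratio cannot be known from the document. They assume that the total sits exactly at the rule's minimum and that pmsampsize does not demand more. If the pmsampsize minimum refers to the total, the training set would reach a shrinkage of about 0.86 to 0.88 against an assumed 0.90.

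The second rule, "2) Total sample size" of at least ten times k, adds no protection: each patient contributes at most one event per endpoint, so the first rule already implies it. Keeping or deleting it changes no result.

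Severity: moderate.

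**What to change.** Revise the sample size section as follows.

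1. State that both the events-per-predictor rule and the pmsampsize minimum must be met in the training set.
2. State whether the retrospective and prospective test sets lie inside or outside the total, and give shares that add up.
3. Because the retrospective data are existing records, cap the predictors instead of enrolling more: k at most training events / 10. With a 70% split this is 0.7 x total events / 10, or at least 14.3 total events per predictor.
4. Apply the 10-20% uplift after that step, so that it remains available for missing data and heterogeneity.

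The cost is one paragraph of wording and no extra patients. The number of predictors allowed falls by up to 30% (1 - 0.70), or by 16-23% if the uplift is intact (1 - 0.84 and 1 - 0.77). The change should be made before model building, which the research plan schedules for January to June 2026.

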**(4) Methods of extraction and allocation of research objects:**

All subjects in this study were derived from real cases in clinical practice.

**(5) Informed consent of the study subject:**

In this study, the cases obtained from the previous process of diagnosis and treatment were used without the application for informed consent.

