#### **Exclusion Criteria:**

This project is a real-world study, including retrospective training, validation, and testing cohorts and prospective testing cohorts. All registries are derived from real cases in clinical practice, and the collected case data should include the following requirements:

1. At the same time, other malignant tumors except HCC were combined;
2. Moderate to severe ascites (ascites on a Child-Pugh score of 3);
3. Received other first-line or second- and third-line systemic therapy (including any regimen of systemic therapy, etc.) or any local therapy (including transcatheter interventional therapy, ablation therapy, internal/external radiotherapy, etc.) and surgical resection or Chinese herbal medicine within 4 weeks prior to TACE combined with targeted immunotherapy.
4. Incomplete data, such as incomplete baseline laboratory examination data, missing or poor quality imaging data, no prognosis information, etc.;
5. Severe liver dysfunction: liver diseases such as decompensated cirrhosis that seriously affect bilirubin levels;
6. Severe comorbidities: such as refractory hypertension (blood pressure is still higher than 150/100 mm Hg after optimal drug therapy), sustained arrhythmia (CTCAE standard grade 2 and above), atrial fibrillation of any degree, Qtc interval prolongation (more than 450 msec in men and more than 470 msec in women), renal insufficiency, etc.;
7. Concomitant human immunodeficiency virus infection (HIV) or acquired immunodeficiency disorder syndrome;
8. pregnant or lactating women;
9. Accompanied by acute or chronic mental disorders (including mental disorders that affect the enrollment, treatment intervention, and follow-up of subjects).

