## **5. The innovation of the project**

This study is a multicenter, retrospective, real-world study of unresectable hepatocellular carcinoma (HCC) undergoing TACE in combination with targeted immunotherapy in the project from January 2016 to June 2025. Baseline imaging data, previous treatments, adverse reactions, clinical outcomes, follow-up imaging data, longitudinal laboratory examination data, etc., were collected to construct a generative model and generate imaging images of the best efficacy after virtual treatment. Combine virtual and real pre-treatment images with other clinical information for accurate prognosis prediction.

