## **6. Research plan and forecast progress**

2025/6-2025/12: Complete the collection, cleaning, and statistical analysis of patients' baseline images, efficacy evaluation, and safety data;

2026/01-2026/06: Complete the construction of the generative model, and evaluate and predict the performance of the model;

2025/06-2026/12: Write a research paper and submit it, and complete the final report.

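### The only consent statement rests on past care, which cannot cover the prospective test cohort(s) named elsewhere, and the protocol disagrees with itself on whether such a cohort exists

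*Protocol*

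**What the plan says.** Protocol, item (5), Informed consent of the study subject, is a single sentence: "In this study, the cases obtained from the previous process of diagnosis and treatment were used without the application for informed consent". It names no cohort and gives no other arrangement.

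Three places describe prospective testing:
- Item (2), Selection of research subjects: "This project is a real-world study, including retrospective training, validation and testing cohorts and prospective testing cohorts".
- Exclusion Criteria, which repeats the description: "including retrospective training, validation, and testing cohorts and prospective testing cohorts".
- Section 3, Research Methodology: "This study is based on a multicenter retrospective cohort including a prospective test cohort".

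Two places point the other way. Section 3 also says: "The data comes from the clinical diagnosis and treatment records of 8 tertiary hospitals from 2016 to 2025". Section 5, on the innovation of the project, describes the whole project as retrospective ("This study is a multicenter, retrospective, real-world study of unresectable hepatocellular carcinoma (HCC"), gives a case window of January 2016 to June 2025, and mentions no prospective cohort.

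**The concern.** A consent statement has to fit every group of patients whose data the study uses. This one gives a single reason for not seeking consent, namely that the care lies in the past. That reason fits archived cases. It does not fit patients identified and followed once the study is under way, and three parts of the protocol say that such patients are included.

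Two things are at stake. The first is the protection of patients who could be asked. The second is the standing of the prospective test data. These are the only test data that the protocol labels as prospective, and the system under test is meant to recommend treatment regimens. If the basis for collecting them is later found not to cover them, their use in validation is open to challenge, and the evidence could then rest on retrospective records alone. That is a risk and not a certainty, but it is cheaper to remove before the data are used than afterwards.

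**Working it through.** No arithmetic beyond dates applies. The check sets the sections side by side.

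**Step 1. Which cohorts does the protocol name?** Retrospective training, validation and testing cohorts, plus prospective testing. The prospective part appears in three places: in the plural in item (2) and the Exclusion Criteria, and in the singular in section 3. The number of prospective cohorts is therefore itself unsettled.

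**Step 2. Does the stated ground hold for each cohort?**

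| Cohort | Ground in item (5): case comes from past care | Result |
|---|---|---|
| Retrospective training, validation, testing | True by definition | Ground applies |
| Prospective testing, in the ordinary sense of the word | Not true at entry | Ground does not apply |

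**Step 3. Does the result depend on how item (5) is read?**
- Broad reading: the sentence governs the whole study. It then uses a ground that is untrue for the prospective patients.
- Narrow reading: the sentence governs past cases only. The section on consent of the study subject then says nothing about a cohort named in three places.

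Under either reading, item (5) does not fit the design in item (2), the Exclusion Criteria and section 3.

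**Step 4. Do the dates leave room for a prospective cohort?**
- Section 5: cases from January 2016 to June 2025.
- Section 3: records from 2016 to 2025, with no month given.
- Section 6: "2025/6-2025/12: Complete the collection, cleaning, and statistical analysis of patients' baseline images", followed by model building from January to June 2026.

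If 2025 in section 3 means the full calendar year, the two windows differ by July to December 2025, which is six months. Patients treated in those months, after the project starts in June 2025, could be prospective under section 3 but fall outside the window in section 5. Both windows close before model building begins in January 2026. Section 6 schedules no enrolment or forward follow-up period.

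**Step 5. What follows?** Two designs remain possible: (a) the later cohort consists of later-dated records and is prospective in name only; or (b) patients are truly entered forward in time. Under (a), items (2) and (5) can be squared only by removing the label. Under (b), item (5) has to change, and so does section 5. Under neither can all the sections stand as written.

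**The case against.** The strongest reply is that item (5) never waives consent for prospective patients. Its grammatical subject is cases from past care, so it can be read as silent on anyone else. Consent pages are also not part of the available text, so a form or an approved waiver may exist. Both points stand. A reader might infer that the protocol plans to enter future patients without asking them. It does not say so, and the finding does not claim it.

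A second reply is that the cohort may not be prospective in substance. Section 3 draws on clinical records, item (7) collects data from electronic records, exclusion 4 removes cases without prognosis information, and section 5 calls the study retrospective. This also stands, as one of two possible answers. It moves the error from item (5) to the word *prospective* in three other places, but an error remains.

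Three further inferences are tempting and unsupported:
- Exclusion 9 speaks of disorders affecting enrolment and follow-up, which might seem to show contact with living patients. One exclusion list serves all cohorts, the retrospective ones included, so it shows nothing about this one.
- One might say that the study would go from one prospective test set to none. Two of the three descriptions are plural, and no cohort size is given.
- One might say that the prospective data will have to be discarded. The documents do not establish that.

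Observational data collection may well qualify for a waiver. That would need its own justification, because the stated one does not reach these patients.

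**Conclusion.** The concern holds as a contradiction within the protocol. The only consent statement shown rests on past care, three sections include prospective testing that this ground cannot cover, and section 5 describes a study with no prospective part. It affects all patients in any truly prospective cohort and none in the retrospective cohorts; the protocol gives no numbers from which to size that group.

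The conclusion assumes that *prospective* carries its ordinary meaning. If it means only later-dated records, no patient lacks a consent basis under item (5), and the error is a label that would lead readers to credit the model with prospective validation it did not have. The conclusion does not depend on whether a consent form exists: if one does, item (5) as worded does not reflect it. This is not a matter for a statistical analysis plan, since the protocol has its own section on consent and that section does not match the design.

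**What to change.** Reconcile item (2), the Exclusion Criteria, item (5), section 3 and section 5, starting with whether a prospective cohort exists.

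- **If it does not** (later-dated records only): remove the prospective label wherever it appears, give one case window, and do not claim prospective validation. Item (5) can then stand.
- **If it does**: limit the no-consent statement in item (5) to the retrospective training, validation and testing cohorts. State that prospective patients enter with informed consent, or under a waiver justified on its own ground and approved by the ethics committee before the first such patient's data are used. Correct section 5 to match, and say whether there is one prospective cohort or more.

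The cost is a change of wording in the protocol and the ethics submission. If consent is sought, add some site time and a few refusals, which would make that cohort slightly smaller. The retrospective work is unaffected.
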